6.2 Subject Exclusion Criteria

- 6.2.1 Patients with a history of stage III melanoma (any primary melanoma with locoregional nodal/subcutaneous disease) treated with surgical resection who subsequently have disease recurrence meeting the criteria for stage IIIC disease.
- 6.2.2 Prior therapy with ipilimumab, other BRAF inhibitors, or MEK inhibitors.
- 6.2.3 Concurrent adjuvant immunotherapy, chemotherapy, or radiotherapy.
- 6.2.4 Current use of a prohibited medication while on dabrafenib (See Section 9, Appendix B).
- 6.2.5 Presence of active gastrointestinal disease or other condition that will interfere significantly with the absorption of drugs.
- 6.2.6 A history of known glucose-6-phosphate dehydrogenase (G6PD) deficiency.
- 6.2.7 Pregnant women and lactating women.
- 6.2.8 A concurrent second malignancy even if it does not require active therapy. Patients with indolent B-cell malignancies will not be eligible. Prior malignancy will be allowed as long as the patient is known to be free of disease for at least 3 years.
- 6.2.9 Uncontrolled intercurrent illness including, but not limited to, ongoing or active infection, symptomatic congestive heart failure, unstable angina pectoris,

cardiac arrhythmia, or psychiatric illness/social situations that would limit compliance with study requirements.

6.2.10 QTc interval > 500 msec, unless a bundle branch block is also present.

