9.2.2 Dose Modifications/Interruption for Toxicity

The severity of adverse events will be graded utilizing the CTCAE version 4.0. Guidelines for dose modifications and interruptions for management of toxicities associated with the study treatment other than fever, neutropenia, rash, hand-foot syndrome, renal dysfunction, and QTc elongation are provided in Table 2. Dose modifications for fever and neutropenia are provided in Table 3 and 4, respectively. Dose modifications for rash and hand foot syndrome are provided in Table 5 and Table 6, respectively. Table 7 contains guidelines for the management of renal insufficiency.

Dabrafenib must be withheld if the QTc exceeds 530 milliseconds. This will be based on the average QTc value of triplicate ECGs. For example, if an ECG demonstrates a prolonged QT interval, obtain 2 more ECGs over a brief period, and then use the averaged QTc values of the 3 ECGs to determine whether the subjects should have study medication withheld.

If the QTc prolongation resolves to Grade 1 or baseline, the subject may be re-started on the study medication if the Investigator and Novartis Medical Monitor agree that the subject will benefit from further treatment.

Table 2: Dose Modification for non-hematologic and hematologic toxicity (except neutropenia)

Non-hematologic and hematologic Toxicity (except neutropenia)	Dose Modification Algorithms ^{a, b, d, e}
Grade 1	Continue dabrafenib at full dose, monitor as clinically indicated.
Grade 2	
For Grade 2 Diarrhea with accompanying risk factors^c Hold dabrafenib until return to ≤ Grade 1, provide supportive care.
 
For all other toxicities: Consider holding dabrafenib until resolution to Grade 1 or baseline; provide supportive care as clinically indicated. Monitoring of laboratory values should occur as clinically indicated.
 
For Grade 2 or higher respiratory symptoms (i.e. cough, dyspnea, hypoxia etc.), evaluation by a CT scan is recommended.

Grade 3	
For Grade 3 toxicity, hold dabrafenib until toxicity is Grade 1 or baseline then reduce dose of dabrafenib by 1 dose level. The subject may be continued at the same dose if, in the judgment of the investigator, the toxicity is considered to be unrelated to dabrafenib. Continue to monitor as clinically indicated.
 
If any Grade 3 toxicity recurs, hold dosing until Grade 1 or baseline, then reduce current dose of dabrafenib by one dose level.

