10.0 EVALUATION DURING TREATMENT/INTERVENTION

10.1 Standard Evaluation

Study participants will be evaluated at the start of each 4 week cycle (\pm 5 days, see Table 8). At these visits, patients will be assessed clinically for melanoma recurrence, toxicity, and performance status. A full physical examination with standard vital signs will also be performed in addition to an ECG and standard laboratories including a CBC, comprehensive metabolic panel, phosphorous, magnesium, and LDH. Radiographic evaluation of disease status will occur at the end of cycles 2 and 4. Dermatological exams (to assess toxicity and to screen for squamous cell carcinoma/keratoacanthomas) will also be done at the completion of cycles 2 and 4 or more frequently as indicated clinically. Ophthalmologic exams will be done at the completion of Cycle 1 and 3 or more frequently as indicated clinically. Dabrafenib will be discontinued after 4 cycles of adjuvant therapy or sooner for disease recurrence or the development of any of the conditions listed in Section 13.0.

After the completion of adjuvant dabrafenib, study participants will undergo active surveillance for disease recurrence. Patients will present at 6 months for a medical history, physical examination with standard vital signs, standard laboratories, and a radiographic evaluation of disease status. This assessment will be repeated every 3 months until the completion of the active follow-up period at 24 months from the date of surgical resection or at recurrence. These assessments and radiographic studies can occur 2 weeks earlier or later without being considered a protocol violation. After 24 months, patients who remain free of disease will continue to undergo routine follow-up and disease assessment at the discretion of their treating physician. Their charts will be reviewed by research staff biannually to monitor for disease relapse and survival and data collection will be limited to survival status until the completion of the study.

Table 8: Pre treatment Evaluation/Evaluation during Treatment

Cycle	Screen ¹	Adjuvant Dabrafenib ¹																Observation ⁿ			
		Cycle 1				Cycle 2				Cycle 3				Cycle 4				6	Every 3 months	24 months/ End of Study	Survival (every 6 months)
		1	2	3	4	5	6	7	8	9	10	11	12	13	14	15	16				
Month																					
Week																					
Medical History	X	X				X				X				X				X	X	X	
Pill Diary		X				X				X				X							
ECOG Performance Status	X	X				X				X				X				X	X	X	

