13.0 CRITERIA FOR REMOVAL FROM STUDY

- Recurrence of the underlying malignancy.
- Unacceptable toxicity not improved with the recommended dose reductions will require cessation of the study drug.
- Development of a secondary malignancy whose systemic treatment would interfere with the study. This does not apply to the development of cutaneous SCC, a known adverse event associated with dabrafenib.
- Development of an intercurrent medical illness in which further administration of the study drug, in the opinion of the Investigator and the treating physician, would be detrimental to the patient.
- Treatment delay of more than 14 days (longer delays must be approved by the Principal Investigator).
- Request of the patient to stop the study.
- Inability of the patient to comply with the requirements of the protocol for treatment or evaluation.

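### With bundle branch block and a baseline QTc above 530 msec, 6.2.10 lets a patient enter while 9.2.2 requires dabrafenib to be withheld, and the restart condition is circular

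*Combined protocol and SAP*

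**What the plan says.** **Entry.** Section 6.2, criterion 6.2.10, excludes "QTc interval > 500 msec, unless a bundle branch block is also present". Neither Section 6 nor Section 8 gives a QTc ceiling for patients who have the block.

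**Withholding.** Section 9.2.2: "Dabrafenib must be withheld if the QTc exceeds 530 milliseconds". The test is an absolute value: "This will be based on the average QTc value of triplicate ECGs". It has no provision for bundle branch block and no comparison with the patient's own baseline.

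**Restart.** The same section: "If the QTc prolongation resolves to Grade 1 or baseline, the subject may be re-started on the study medication". The sentence goes on to require that the investigator and the company's medical monitor agree the patient will benefit.

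**No other QTc dosing rule.** Section 9.2.2 sends to Table 2 the toxicities "other than fever, neutropenia, rash, hand-foot syndrome, renal dysfunction, and QTc elongation are provided in Table 2". Tables 3 to 7 deal with the other listed exceptions. None deals with QTc, so the paragraphs just described are the only QTc dosing instruction.

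**ECG schedule.** Section 8.3 asks for an ECG within 4 weeks of study start. Section 10.1 repeats it at the start of each cycle: "A full physical examination with standard vital signs will also be performed in addition to an ECG and standard laboratories". Table 8, note i, lets a screening ECG from within 7 days stand in for the one at Cycle 1, week 1.

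**Consequences of a hold.** Section 13.0 lists as a ground for removal "Treatment delay of more than 14 days (longer delays must be approved by the Principal Investigator"). Section 14.0 replaces only patients who withdraw consent before month 24 and before relapse.

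**The concern.** Patients with bundle branch block are the one group that the protocol deliberately lets past its QTc entry limit. The withholding rule is then written as if that exception did not exist. If such a patient's usual QTc is above the withholding threshold, the site holds two instructions that give opposite answers for one ECG: the patient qualifies for treatment, and treatment must not be given. The restart condition does not settle it, because one of its two arms refers back to the same baseline value.

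At stake is a mandatory safety rule that cannot be applied consistently in this group, and the use of a place in a 23-patient trial by someone whom the protocol admits but, read literally, does not allow to be dosed.

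**Working it through.** The plan gives no figure to reproduce here, so the check applies the two rules to the same patient.

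**Inputs.** Entry limit 500 msec, waived with bundle branch block (6.2.10). Withholding above 530 msec (9.2.2). Restart at Grade 1 or baseline (9.2.2).

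**Rules.** Let B be the baseline QTc and Q a later reading, both in msec.

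- Eligible on QTc: B ≤ 500, or bundle branch block present.
- Withhold: Q > 530.
- Restart may be considered: Q back to Grade 1, or Q back to B.
- Conflict at entry: the patient is eligible and Q = B already meets the withholding test.

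Without the block, eligibility means B ≤ 500. Since 500 < 530, no eligible patient meets the withholding test at baseline. With the block, eligibility on QTc is always met, so a conflict arises exactly when B > 530.

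| Baseline QTc (msec) | No block | Block present |
|---|---|---|
| 490, 500 | eligible, not held | eligible, not held |
| 501, 515, 530 | excluded | eligible, not held |
| 531, 550 | excluded | **eligible, must be held** |

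**Restart, block present.**

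- B = 515. A reading rises above 530 and the drug is held. It returns to 515: the baseline arm is met, and 515 is not above 530. The rules agree.
- B = 550. The drug is held. The reading is at, or returns to, 550: the baseline arm is met, but 550 > 530, so the withholding rule still applies. One value triggers the hold and satisfies the condition for ending it.

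The Grade 1 arm need not be examined. The two arms are alternatives, so the baseline arm is enough to make the condition circular.

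**Does another section resolve it?**

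- Section 8.3 requires the ECG but sets no limit.
- Section 10.1 and Table 8 schedule ECGs without saying how 9.2.2 applies to the entry value. Where note i applies, the next scheduled ECG after screening is at Cycle 2, and the text does not say whether the screening value counts for withholding.
- Section 13.0 could turn a lasting hold into removal after 14 days, unless the Principal Investigator approves a longer delay. That is a consequence of the conflict and does not resolve it.
- Section 14.0 keeps the patient among the 23 unless consent is withdrawn before month 24 and before relapse.

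None of these says which rule governs.

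**The case against.** The strongest reply is that an entry limit and an on-treatment limit answer different questions and need not be equal. That is right. A reader might infer that 6.2.10 and 9.2.2 contradict each other generally, or for every patient with bundle branch block. The table shows otherwise: outside the group with the block and a baseline above 530 msec, entry, withholding and restart fit together. Nor is the interval from 501 to 530 msec evidence of an error. A patient who enters at or below 500 and later drifts into it is under the 9.2.2 procedure, which calls for two further ECGs and an average when a tracing shows prolongation.

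A second reply is that restart is permissive and needs two parties to agree. This also stands. A reader might infer that the protocol compels dosing above 530 msec, and it does not. But the agreement applies to restart only. It does not address entry or the first dose, and it does not say how to read a baseline that is itself above the threshold.

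Third, 6.2.9 excludes uncontrolled intercurrent illness, with cardiac arrhythmia among its examples, so an investigator might decline such a patient. It sets no QTc value, however, and 6.2.10 expressly contemplates admitting patients with the block.

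Two further inferences lack support. One is that the entry ECG ought to be a triplicate average: 9.2.2 introduces averaging for the withholding decision, and no section promises it at screening. The other is that the primary endpoint is compromised. Section 14.0 deliberately follows patients by intention to treat. The rule of 9 or more out of 23 has an exact binomial type I error of 0.078 at a true rate of 24% and power of 0.911 at 51%, within the planned 0.10 and 0.10. Those figures depend only on 23, 9 and the assumed rates. The documents give no count of affected patients from which to compute a shift in the true rate.

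**Conclusion.** The point holds in a narrow form. For a patient with bundle branch block and a baseline QTc above 530 msec, 6.2.10 permits entry, 9.2.2 requires withholding at that same value, and returning to baseline meets the restart condition while the withholding rule still applies. No other section reconciles them.

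This rests on reading 6.2.10 as a complete waiver of the limit when the block is present, and 9.2.2 as applying to every patient. Both are the plain sense of the text. The number affected is probably small. The documents give no frequency for the block or for QTc values of this size, so the only figure available is that each such patient is one of 23. The point is worth correcting because two stated safety rules give opposite answers for one ECG and the correction is cheap. I take no view on which threshold, exception or restart condition is right.

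**What to change.** The sponsor's medical team should reconcile 6.2.10 with the withholding and restart text of 9.2.2, so that eligibility, withholding and restart give consistent answers for patients with bundle branch block, including those whose baseline QTc exceeds 530 msec. The outcome should then be carried to the eligibility checklist named in Section 15.1. The values and the form of the reconciliation are for that team to decide.

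The cost is a short amendment: about one sentence in each of 6.2.10 and 9.2.2, and a line on the checklist. The sample size, the decision rule and the analysis need no change.

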6.3 Inclusion of Women and Minorities

Both men and women and members of all races and ethnic groups are eligible for this trial.

7.0 RECRUITMENT PLAN

Patients will be recruited through the Melanoma Disease Management Team of the Memorial Sloan-Kettering Cancer Center. Melanoma tumors are routinely genotyped for *BRAF* at MSKCC. The Melanoma/Sarcoma service and the Melanoma Disease Management Team each hold weekly interdepartmental meetings to identify study participants for open clinical trials.

8.0 PRETREATMENT EVALUATION

The following procedures and assessments must be performed prior to treatment start:

8.1 At anytime prior to the start of the study

- Histologic confirmation of melanoma by a MSKCC pathologist.
- Assessment of *BRAF* mutational status (either primary or regional metastases) by CLIA certified laboratory.

8.2 Within 90 days of the start of study

- Complete surgical resection of Stage IIIC disease. This can be completed either at MSKCC or at an outside institution.
- Patients may have adjuvant radiation therapy but all treatment must be completed and patients adequately recovered before beginning dabrafenib.

8.3 Within 4 weeks of the start of the study

- Written Informed Consent
- A contrast-enhanced CT or MRI of the brain
- ECG

8.4 Within 2 weeks of the start of the study

- Updated medical history and physical examination
- A complete skin examination by dermatology or a consenting medical oncologist.
- An eye examination by ophthalmology
- Laboratory studies including a CBC with differential; comprehensive metabolic panel; serum phosphorous, magnesium and LDH levels.

- A serum pregnancy test for woman of child-bearing potential.
- Appropriate radiologic assessment to assure no evidence of disease. In general, this will involve a CT scan (with contrast) of the chest, abdomen and pelvis; if the patient is not able to undergo a CT scan, a MRI with and without gadolinium may be used. For patients with a primary melanoma below the knee, a PET scan with a non-contrast chest CT will also be acceptable.

9.0 TREATMENT/INTERVENTION PLAN

9.1 Adjuvant Dabrafenib

Treatment will be administered on an outpatient basis. Reported adverse events and potential risks are described in Section 11. Appropriate dose modifications for dabrafenib are described below in Section 9.2. No investigational or commercial therapies other than those described below may be administered with the intent to treat the patient's malignancy.

If all eligibility criteria are met, study participants will self-administer dabrafenib by mouth at a dose of 150 mg twice a day. Four weeks of treatment is one full cycle. After each cycle (\pm 5 days) the study participant will be seen in clinic for a complete clinical evaluation as detailed in section 10.0. A pill diary will be provided to the patient and will be reviewed at the completion of each cycle (Appendix C). This will be used to assure compliance with the regimen. In the absence of treatment delays due to adverse event(s), dabrafenib will continue for 4 cycles or until one of the criteria listed in Section 13 apply.

9.2 Dose Modification

9.2.1 Dose Modifications Algorithm

Management of symptomatic adverse drug reactions may require temporary interruption and dose reduction of dabrafenib treatment. Table 1 describes the dose levels to be used for any necessary dose modifications.

Table 1: Dabrafenib Dose Reduction Algorithm

Dose Level	Dose/Schedule
0	150 mg BID
-1	100 mg BID
-2	75 mg BID
-3	50 mg BID

9.2.2 Dose Modifications/Interruption for Toxicity

The severity of adverse events will be graded utilizing the CTCAE version 4.0. Guidelines for dose modifications and interruptions for management of toxicities associated with the study treatment other than fever, neutropenia, rash, hand-foot syndrome, renal dysfunction, and QTc elongation are provided in Table 2. Dose modifications for fever and neutropenia are provided in Table 3 and 4, respectively. Dose modifications for rash and hand foot syndrome are provided in Table 5 and Table 6, respectively. Table 7 contains guidelines for the management of renal insufficiency.

Dabrafenib must be withheld if the QTc exceeds 530 milliseconds. This will be based on the average QTc value of triplicate ECGs. For example, if an ECG demonstrates a prolonged QT interval, obtain 2 more ECGs over a brief period, and then use the averaged QTc values of the 3 ECGs to determine whether the subjects should have study medication withheld.

If the QTc prolongation resolves to Grade 1 or baseline, the subject may be re-started on the study medication if the Investigator and Novartis Medical Monitor agree that the subject will benefit from further treatment.

Table 2: Dose Modification for non-hematologic and hematologic toxicity (except neutropenia)

Non-hematologic and hematologic Toxicity (except neutropenia)	Dose Modification Algorithms ^{a, b, d, e}
Grade 1	Continue dabrafenib at full dose, monitor as clinically indicated.
Grade 2	
For Grade 2 Diarrhea with accompanying risk factors^c Hold dabrafenib until return to ≤ Grade 1, provide supportive care.
 
For all other toxicities: Consider holding dabrafenib until resolution to Grade 1 or baseline; provide supportive care as clinically indicated. Monitoring of laboratory values should occur as clinically indicated.
 
For Grade 2 or higher respiratory symptoms (i.e. cough, dyspnea, hypoxia etc.), evaluation by a CT scan is recommended.

Grade 3	
For Grade 3 toxicity, hold dabrafenib until toxicity is Grade 1 or baseline then reduce dose of dabrafenib by 1 dose level. The subject may be continued at the same dose if, in the judgment of the investigator, the toxicity is considered to be unrelated to dabrafenib. Continue to monitor as clinically indicated.
 
If any Grade 3 toxicity recurs, hold dosing until Grade 1 or baseline, then reduce current dose of dabrafenib by one dose level.

Grade 4	
Discontinue dabrafenib. Continue to monitor as clinically indicated, and provide supportive care as needed
 
If in the investigator's judgment the toxicity is unlikely to recur then, hold until toxicity is Grade 1 or baseline, then reduce dose of dabrafenib by 1 dose level. If Grade 4 toxicity recurs after dose reduction, discuss continuation of study drug with the Novartis Medical Monitor.

- a. The minimum dose is 50mg BID. If a subject requires dose reduction below 50mg BID then the subject must be discontinued from study medication.
- b. For adverse events of abdominal pain or suspected pancreatitis, amylase and lipase laboratory samples should be collected.
- c. Risk factors for cancer treatment-induced diarrhea include: fever, orthostatic symptoms (i.e. dizziness), abdominal pain/cramping, or weakness.
- d. If the subject has a Grade 3 or 4 laboratory abnormalities that, in the judgment of the investigator, is not considered clinically significant, dose modification is not required.
- e. For subjects who develop symptoms associated with uveitis including blurry vision, eye pain or erythema ophthalmologic consult is required.

Table 3: Dose Modification and Guidelines for Management of Neutropenia

Grade	ANC value K/mcl	Management of Neutropenia	Dabrafenib Dose Adjustment
1	1.5 to LLN	
 Monitor per protocol study calendar. 	
 Continue at current dose
2	1.0 to <1.5	
 Re-check ANC in 1 week. If improvement to grade 1, continue to monitor per study calendar. If stable at grade 2, monitor ANC every 2 weeks until resolution to grade 1 or until stable for 4 weeks If worsens to grade 3 or 4 follow below. 	
 Any occurrence: continue at current dose
3	0.5 to <1.0	
 Re-check ANC at least weekly during dose interruption. If resolved to grade 1, re-check ANC 3 days after rechallenge with dabrafenib and then 1 week later. 	
 Any occurrence: hold until return to grade 1, then reduce one dose level 1st recurrence: discontinue dabrafenib or hold until return to grade 1, then reduce one dose level 2nd recurrence: discontinue dabrafenib.
4	< 0.5	
 Re-check ANC at least weekly If resolved to grade 1, re-check ANC 3 days after rechallenge with dabrafenib and then 1 week later. 	
 Discontinue or hold until return to grade 1, then reduce dabrafenib by one dose level. 1st recurrence discontinue dabrafenib

Table 4: Dose Modification and Guide lines for Manage ment of Fever

	Definition	Dose Mod ificati on Algorithms	Dabrafeni b Dose Adjustment
Co mplicated fever. ($\geq 38.5^{\circ}\text{C}$ or 101.3°F)	Grade ≥ 3 or any grade with signs and symptoms including; rigors , dehydration, hypotension, dizzines s or wea kness	
 • Subject must be evaluated in clinic • Labs : Obtain blood sample to assess ANC, s erum creat inine and BUN if samp le was not collected within 3 days of the fever. • Evaluate for signs and symptoms of infect ion and cons ider work up as clin ically indicated. • If signs and symptoms of dehydration occur, cons ider intravenous hydration. • When restarting drug, adminis ter acetaminophen 500 mg or ibuprofen 400 mg (or suitable alternative) prophylactically BID with study drug for 2-3 days. • Re-check ANC 1 week after the start of fever; encourage subject to take oral temperature daily for 4 weeks after restarting dabrafenib. 	
 • Interrupt dabrafenib immed iately and hold until fever resolves to $<38.0^{\circ}\text{C}$ or 100.4°F and accompanying symptoms resolve • At rechallenge reduce dose of dabrafenib by one dose level.
Uncomp licated Fever ($\geq 38.5^{\circ}\text{C}$ or 101.3°F)	defined as grade ≤ 2 without signs and symptoms as des cribed above	
 • Encourage oral hydration. • If subject is seen in the clinic, obtain blood sample to assess ANC, s erum creat inine and BUN if samp le was not collected within 3 days of the fever • Evaluate for signs and symptoms of infect ion and cons ider work up as clin ically indicated. • If signs and symptoms of dehydration occur, follow a lgorithm for complicated fever. • When restarting drug, adminis ter acetaminophen 500 mg or ibuprofen 400 mg (or suitable alternative) prophylactically BID 	
 • Hold until fever resolves to $<38.0^{\circ}\text{C}$ or 100.4°F. • Dabrafenib may be restarted at the original dose level or reduced one dose level as clin ically indicated.

		with study drug for 2-3 days. 
 Re-check ANC 1 week after the start of fever; encourage subject to take oral temperature daily for 4 weeks after restarting dabrafenib. 	
--	--	--	--

1. If fever does not recur after 3 days, prophylactic antipyretics may be discontinued or tapered.

Table 5: Guide lines for Skin Rash Management

Skin Toxicity Grade (CTCAE v 4.0)	Guideline for Management	Dose Reduction
1	Topical corticosteroids (mometasone, betamethasone, or fluocinonide creams)	None
2	As for grade 1, with the addition of diphenhydramine 50 mg bid, oral prednisone (short course)	None: if unacceptable to subject or medically concerning then hold until recovery to ≤Grade 1. Restart at same dose.
≥3		Hold until recovery to ≤Grade 1. Then reduce the dose by one dose level.

Table 6: Guide lines for Hand-Foot Syndrome

Grade	Occurrence	Dose Modification
Grade 1: Minimal skin changes or dermatitis (e.g., erythema, edema, or hyperkeratosis) without pain	Any occurrence.	Continue treatment with dabrafenib and start topical therapy ^a for symptomatic relief.
Grade 2: Skin changes (e.g., peeling, blisters, bleeding, edema, or hyperkeratosis) with pain; limiting instrumental ADL	1st occurrence.	Continue treatment with dabrafenib and start topical therapy ^a for symptomatic relief. Instruction on life-style modifications should also be given. ^b If no improvement within 28 days, see below
	No improvement within 28 days or additional occurrence.	Interrupt dabrafenib treatment until toxicity resolves to Grade 0-1. ^c When resuming treatment, decrease dabrafenib dose by one dose level. Continue topical therapy ^a for symptomatic relief. Instruction on life-style modifications should also be given. ^b
Grade 3 or intolerable grade 2: Severe skin changes (e.g., peeling, blisters, bleeding, edema, or hyperkeratosis) with pain; limiting self care ADL	1st or 2nd occurrence.	Interrupt dabrafenib treatment until toxicity resolves to Grade 0-1. ^c When resuming treatment, decrease dabrafenib dose by one dose level. Continue topical therapy ^a for symptomatic relief. Instruction on life-style modifications should also be given. ^b
	3rd occurrence.	Discontinue dabrafenib treatment.

a. Topical therapy includes the following options; keratolytics (e.g. urea 40%), high potency corticosteroids (fluocinonide, clobetasol) oral analgesia (non-steroidal anti-inflammatories or narcotics)

b. Life style modifications include; avoidance of excessive temperatures, exercise, and ill-fitting clothing/shoes. Use of soft slippers (Tempurpedic or Crocs), friction-relieving measures (calfskin,

- gels).
 c. HSRF usually resolves within 2-4 weeks of drug cessation.

Table 7: Renal Insufficiency Guidelines

Creatinine	Guidelines for Management
For subjects with serum creatinine increase > 0.2 mg/dL but ≤ 0.5 mg/dL above baseline:	
 1. Continue dabrafenib and re-check serum creatinine within 1 week 2. If subject has fever ($T \geq 38.5C$): treat pyrexia as per guidelines (please note NSAIDs can induce renal insufficiency, especially in subjects with dehydration); encourage oral fluids 3. If elevation in serum creatinine persists beyond 1 week, please contact medical monitor
For subjects with serum creatinine rise > 0.5 mg/dL above baseline or serum creatinine > 2 mg/dL:	
 1. Interrupt dabrafenib 2. If subject has fever ($T \geq 38.5C$): treat pyrexia as per guidelines (please note NSAIDs can induce renal insufficiency, especially in subjects with dehydration); consider IV hydration 3. Follow serum creatinine at least twice weekly (or consider hospitalization if serum creatinine cannot be monitored frequently) 4. Consider renal consultation 5. If serum creatinine returns to baseline, may restart study treatment at the same dose, or reduced by one dose level at the investigator's discretion. 6. Consider renal biopsy if clinically indicated, for example: 
 a. Renal insufficiency persists despite volume repletion b. Subject has new rash or signs of hypersensitivity (such as elevated eosinophil count) 7. Prior approval of Medical Monitor is required to re-initiate therapy if 
 c. Subject's serum creatinine has not returned to baseline d. There is evidence of thrombotic microangiopathy

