5.3 Administration of Dabrafenib

Dabrafenib will be dosed at 150 mg twice a day by mouth. Patients are instructed to take 150 mg in the morning and 150 mg in the evening, approximately 12 hours apart. Dabrafenib should be administered under fasting conditions, either 1 hour before or 2 hours after a meal. If a study participant vomits after a dose, the patient should be instructed not to retake the dose and should take the next dose at its scheduled time. If a dose is missed, it can be taken up to 6 hours prior to the next dose to maintain the twice daily regimen. Instructions for dose modifications can be found in Section 9.

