11.4.1 Likely Toxicities (>10%)

- Anemia
- Diarrhea
- Nausea
- Vomiting
- Anorexia
- Constipation
- Rash
- Actinic keratosis
- Hyperkeratosis
- Squamous Cell Carcinoma (SCC) of the skin
- Alopecia
- Pruritus
- Fatigue
- Headaches
- Pyrexia
- Syncope
- Arthralgias
- Myalgias
- Chills

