11.7 Squamous Cell Carcinoma of the Skin

BRAF inhibition is associated with the development of squamous cell carcinoma (SCC) of the skin, keratoacanthomas (KA) and cutaneous papillomas [39]. The median time to appearance is approximately 8 weeks into treatment. All suspicious lesions should be completely resected by a dermatologist and submitted for pathologic review. A dose reduction is not indicated for this adverse event.

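### For a drug-related cutaneous squamous cell carcinoma graded 3 or higher, Table 2 in Section 9.2.2 and Section 11.7 contradict each other on dose reduction

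*Combined protocol and SAP*

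**What the plan says.** Section 5.3 tells the site where dose changes are laid down: "Instructions for dose modifications can be found in Section 9". Section 9.1 narrows that to Section 9.2.

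Section 9.2.2 makes Table 2 the default table for toxicities attributed to treatment. It covers those "other than fever, neutropenia, rash, hand-foot syndrome, renal dysfunction, and QTc elongation are provided in Table 2". The Table 2 title excepts only neutropenia, and none of footnotes a to e mentions SCC. The Grade 3 row reads: "For Grade 3 toxicity, hold dabrafenib until toxicity is Grade 1 or baseline then reduce dose of dabrafenib by 1 dose level". The same dose may be kept if the investigator judges that "the toxicity is considered to be unrelated to dabrafenib". For a repeat event the row adds: "If any Grade 3 toxicity recurs, hold dosing until Grade 1 or baseline, then reduce current dose of dabrafenib by one dose level". The Grade 4 row says to discontinue or, where the investigator thinks recurrence unlikely, to hold and come back one level lower.

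Section 11.7 deals with SCC of the skin, keratoacanthoma and cutaneous papilloma under BRAF inhibition. It asks for complete resection of suspicious lesions and ends: "A dose reduction is not indicated for this adverse event". It sets no grade limit and does not mention Section 9.

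Section 11.4.1 lists "Squamous Cell Carcinoma (SCC) of the skin" among the drug-related toxicities seen in more than 10% of patients. Section 13 exempts cutaneous SCC from the second-malignancy removal criterion because it is recognised as an effect linked to dabrafenib.

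**The concern.** An investigator who follows Sections 5.3 and 9.1 goes to Section 9.2, finds no exemption for SCC, and reduces the dose after a Grade 3 lesion. An investigator who follows Section 11.7 does not. Both are complying with the protocol. The dose given after such an event would then depend on which section was read, and neither course could clearly be called a deviation. The event is one the protocol anticipates: Section 11.7 puts median onset at about 8 weeks, and Section 10.1 schedules dermatology examinations that screen for it. What is at stake is consistent dosing, and a clear reading of exposure and compliance, in the patients concerned.

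**Working it through.** No figure in the plan needs to be reproduced. The check is a comparison of text, followed by a short calculation of how far it could reach.

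**Which table covers SCC?** The six exclusions in Section 9.2.2 are fever, neutropenia, rash, hand-foot syndrome, renal dysfunction and QTc. SCC and keratoacanthoma are not among them, so Table 2 applies. Reading SCC into Table 5 as a skin toxicity would not help, because its row for Grade 3 and above also orders a hold and a one-level reduction.

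**Comparison by grade, for a lesion judged drug-related**

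| Grade | Table 2 | Section 11.7 | Conflict on reduction? |
|---|---|---|---|
| 1 | Continue at full dose | No reduction | No |
| 2 | Consider a hold; no reduction ordered | No reduction; silent on holds | No |
| 3 | Hold, then down one level; again on recurrence | No reduction; silent on holds | Yes |
| 4 | Discontinue or, if unlikely to recur, hold and go down one level | No reduction; silent on holds and on discontinuation | Yes, for the restart option |

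**Does any clause in Table 2 resolve it?**
- The unrelated-toxicity exception in the Grade 3 row would not ordinarily apply, because Sections 11.4.1 and 13 treat SCC as associated with the drug.
- Footnote d covers laboratory abnormalities only.
- Table 2 does not refer to Section 11.7, and neither says which prevails. By contrast, Section 11.5 sends the reader to Table 4 and Section 11.6 to Table 7.

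**Size of one step.** From Table 1, one level down from the starting dose is 150 to 100 mg BID: (150 − 100) / 150 = 0.33, a one-third cut. Section 11.7 would leave the dose unchanged.

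**How many patients?** Section 14.0 plans 23 patients, and Section 11.4.1 gives a frequency above 10%. Assuming that this earlier-trial frequency carries over to a course of 4 × 28 = 112 days:
- expected patients with an SCC of any grade: more than 23 × 0.10 = 2.3;
- chance of at least one, if patients are independent: more than 1 − 0.9^23 = 0.91.

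Both figures are for SCC of any grade. The conflict concerns only Grade 3 or higher. The documents assign no grade to SCC and do not reproduce the CTCAE definitions, so the affected fraction may lie anywhere from 0 to 100% of these cases. The expected number affected cannot be narrowed from the documents.

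**The case against.** The best reply is that a specific rule prevails over a general one. Section 11.4 introduces the event sections as guidance on management and prevention, Section 11.7 speaks directly to SCC, and Section 13 also sets SCC apart. That reading is plausible, but it is not written down. Sections 5.3 and 9.1 name Section 9 and Section 9.2 for dose changes; Section 9.1 mentions Section 11 only for reported events and risks. Section 13 shows that the authors wrote an SCC exemption where they wanted one, and Section 9.2.2 contains none.

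A second reply is that Table 2 leaves relatedness to the investigator, and an association with the drug does not settle causality lesion by lesion. This stands in part: the exception is not closed off for every lesion. It would still be an odd route for an event the protocol itself lists as drug-related.

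A third reply is that the conflict may never arise, since no SCC may be graded 3 or higher. The documents cannot exclude that, and it limits the weight of the point.

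Stronger readings are tempting and are not supported:
- A reader might infer that the sections give opposite orders for every SCC. They do not: nothing conflicts on reduction at Grades 1 and 2, and because Section 11.7 is silent on holds, a hold alone contradicts nothing.
- A reader might follow Table 1 down from 150 through 100 and 75 to 50 mg BID and then to discontinuation. That needs four Grade 3 events in one patient, with three holds and restarts between them, in a 16-week course with median onset near week 8. The documents do not say that SCC recurs within a patient.

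**Conclusion.** The contradiction is real and narrow. For a drug-related cutaneous SCC or keratoacanthoma graded 3 or higher, Table 2 calls for a reduced dose on restart and Section 11.7 says no reduction is indicated. Nothing in the protocol says which governs. The conclusion rests on the wording alone and on the lesion being judged drug-related, as the protocol's own lists suggest.

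The practical reach is unknown. A reader might take 2.3 patients, or a 0.91 chance, as the number affected or the probability of the conflict. Neither is: both count SCC of any grade and assume that the earlier-trial frequency applies to this adjuvant course. Nor does the point touch the efficacy inference as designed: the 24-month relapse-free endpoint, the rule of 9 or more successes in 23, and the sample size stand as they are. It is an inconsistency in dosing instructions that should be corrected. This review takes no view on which instruction is right.

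**What to change.** Reconcile Section 9.2.2 and Table 2 with Section 11.7 so that one rule for cutaneous SCC and keratoacanthoma appears in both places, each referring to the other. If Section 11.7 is the intended rule, name these lesions among the exclusions in Section 9.2.2 and point to Section 11.7. If Table 2 is intended, correct the closing sentence of Section 11.7 and point to Table 2. The reconciled text should also say whether a hold applies, since Section 11.7 is silent on it. The choice belongs to the sponsor and the safety team.

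The cost is an amendment of a sentence or so plus the cross-references. No statistical section needs to change.
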